## Micro-Randomized Trials (MRTs)

Phase 2 will consist of rapid deployment of micro-randomized trials (MRTs) on both MHA and TS platforms to understand what factors and engagement strategies may lead to increased engagement with digital mental health services. As with Phase 1, we are requesting a waiver of consent for these activities Data collected in Phase 2 MRTs will include meta-data and content data. Meta-data includes behaviors such as click throughs to pages and links, time spent on a page, mouse/cursor movement between screening and material selections on a webpage, number of text interactions, time texting, and time between texts. These data are collected on the order of milliseconds (cursor hovers), seconds (clicks), minutes (page views, time between sessions), and hours, days, weeks (number of texts, visits over time). Content data includes survey measures, transcripts (TS only), demographics, type of articles/resources accessed. All data types are routinely collected by MHA and TS. Both MHA and TS, as part of routine practice and as part of their terms and conditions, explain to consumers that their information may be used for research purposes and shared with researchers in academic settings to better understand mental illness and for quality improvement purposes.

We will perform micro-randomized trials (MRTs) using methodology of simultaneous A/B trials. In these trials, full access to all tools, resources, and other information provided by the platforms for users will be maintained for participants in the trials. Participants will not lose access to any information or features of the sites of which they previously had access to. Already existing features, tools and/or information may only be modified in their visual presentation on the platforms. The MRTs will be deployed on both MHA and TS, with some requiring coordination across both platforms, throughout Phase 2. The following describes the type and scope of activities that will be conducted for each organization:

## **Mental Health America**

MHA trials will focus on modifying current features on the website. In the past, MHA has conducted experimental user testing on engagement such as modifying tone, placement, and medium (written vs audio) of education materials, modifying language and linkages to services like telehealth partners, adding relevant links to other materials, and improving the formatting of articles for clarity. The future trials use this testing as a foundation for experimentation. For example, one focus of a future trial will be to present different online resources to MHA site users after they complete a survey that evaluates where they are in their help-seeking journey.

APPLICATION IRB Protocol

### **Talkspace**

Trials conducted with Talkspace may focus on similar elements of user design in search of understanding better what design and presentation of information best helps potential and actual clients get the appropriate care that is the best fit for them and where they are at in their mental health journey. Strategies may include modifying informational pages in their visual presentation, adjusting the onboarding process to address areas of likely attrition, integrating new tools and information into treatment interface.

We have uploaded a table of example potential MRTs to Zipline to provide further clarification (File Name: MHATS Proposed MRTs). While we are providing these examples, we request flexibility to implement MRTs within the scope of the project (understanding what factors and engagement strategies lead to increase utilization of digital mental health services).

## Data Transfer, Identifiability, and Analysis

All procedures regarding data transfer, identifiability, and analysis in Phase 2 are the same as those in Phase 1.

## Focus Groups

Phase 2 focus group procedures are the same as those in Phase 1.

Talkspace will host focus groups in Phase 2 where participants are invited based on their previous experience with therapy. TS consumers that have recently signed up for services will receive an invitation to complete a brief screening survey about previous engagement with therapy and demographic questions. Invitations to participate in the focus groups will be extended to individuals based on their responses to the screening survey. For example, individuals with no previous experience in the provided to a focus group with other individuals with no previous experience in therapy. All individuals that respond to the survey will receive an invitation to a focus group (the specific focus group they are invited to will depend on their response to the survey). While the focus group the individual is invited to will be based on their response to the screening survey, the structure, content, and procedures for the focus groups are all the same as previously described in Phase 1. As part of the informed consent process, focus group participants will have the option to give consent for their responses during the focus group to be linked to data on their usage of the Talkspace platform (e.g., engagement with TS platform, number of texts sent, response to push notifications). All data will be anonymized prior to transfer from TS to UW using the procedures outlined previously.

## Phase 3

## Phase 3:

Study 1 (SMART): We will use a Sequential Multiple Random Assignment Trial (SMART) with an expected 50,000 users, with the goal of optimizing engagement strategies so that web users engage with MHA resources most relevant to their needs, including psychoeducation, links to treatment providers, or self-help tools. Participants will be randomized to type of screening results language, with conditions including results-as-usual, or tailoring by: 1) demographics (race, LGBTQ status, age) or 2) mental health severity (screening results) & perceived need. Subsequent randomization will determine whether single-item self-help tools embedded in content pages serve to engage users in active mental health strategies. Participants will be MHA consumers who land on the PHQ-9 mental health test page on the MHA website.

#### **Recruitment Procedures**

No recruitment measures will be put in place, as we will be collecting data on participants who enter the PHQ screening page naturalistically.

## **Consent Procedure**

As MHA consumers will be engaging with the website naturalistically, and the terms and conditions in the site include provisions around the use of user data for research, we will not be collecting formal consent from participants.

## Screens/Surveys

PHO-9

Mini quiz/Next Steps Quiz (DOC: Study 2 Next steps brief survey) – we request flexibility with the language used for these questions

#### Metadata collection

We will use metadata, which consists of passive data that is curated from each website and describes how consumers initiate, use and disengage from DMH services. Metadata includes behaviors such as click throughs to pages and links, time spent on a page, mouse/cursor movement between screening and material selections on a webpage, number of text interactions, time texting, and time between texts. These data are collected on the order of milliseconds (cursor hovers), seconds (clicks), minutes (page views, time between sessions), and hours, days, weeks (visits over time).

## **Randomization sequence**

The drafted randomization sequence is outlined on the MHA SMART Flow.pdf uploaded to zipline. Participants will be randomized first between a standard demographics survey to start or demographics along with a mini quiz focusing on asking a participant's primary website action intention (e.g., reading more about depression, connecting with therapists, using a DIY tool) and perceived need to do something to improve their mental health. Participants will then be randomized to types of screening results pages, with combinations of tailored responses and resources based on their responses to the demographics quiz and/or the mini quiz. For instance, if the participant chooses to continue to visit further content, they will be randomized to conditions of different presentations of a DIY question or tool on the page. Length of engagement, bounce rates, and other variables listed under metadata collection will be used to examine the impact of tailoring on engagement, which conditions and combinations of conditions result in increased engagement, and how the use of DIY tools impact engagement.

## Study 2

As previously proposed in Aim 3, we have developed an AI tool that uses machine learning / NLP / AI methods to personalize and tailor an intervention to improve engagement and completion outcomes. We focus on a specific, popular DIY tool (~10,000 users /month) that teaches cognitive restructuring. Our pilot work found that (1) engagement and completion rates on DIY tools can be low, and (2) a pilot AI tool had significantly higher engagement and completion rates. These differences may arise due to AI support, UI/UX/design differences, other factors, or a combination thereof. Additionally, the efficacy of the digital tool to improve mental health functioning is unknown. Study 2 will recruit 300 participants who will be randomly assigned to one of three groups for a longitudinal month-long study: twice-weekly DIY tool use with AI, without AI, or a control group.

## **Recruitment Procedures**

Potential participants will be shown an invitation to participate in this portion of the study and displayed on the screening results page for users after the PHQ-9 and GAD-7 mental health tests. If consumers are interested in learning more, they can respond to the invitation by clicking on a link, which will direct them to a landing page (displayed via REDCap survey) with more information about the study and the screening survey.

Screens/Surveys: All measures in this section will be completed using REDCap – refer to DOC: DIY Study – Measures for all measures listed in this section, and refer to DOC: Demographic questions for the demographics measure. Participants will receive links to complete these surveys via email and/or text message using Twilio, a REDCap extension that allows for SMS communication with participants. Participants will complete an initial screening assessment to determine eligibility, and then complete the same list of measures for 4 weeks while using intervention (consistent to each condition), an exit survey at week 5 and follow up measures consistent with the weekly measures at week 8 follow up. All participants will be asked to complete the demographics measure in addition to the measures included in the first week's battery of assessments.

Participants will be asked to complete the following measures in the screener:

- PHQ-9

- GAD-7
- Hopefulness Item
- Emotion Mechanisms

At the end of weeks 1-4 and week 8 follow up, participants will be asked to complete the following measures, some measures adjusted depending on condition:

- Questions Post DIY AI [DIY Tool, AI condition ONLY]
- PHQ-9
- GAD-7
- Hopefulness Item
- Emotion Mechanisms
- Competencies of Cognitive Therapy Scale Self Report
- Tool Use (sustain) [DIY Tool, No AI condition ONLY WEEKS 1-4, BOTH DIY TOOL CONDITIONS at WEEK 8]
- Tool Use (AI) [DIY Tool, AI condition ONLY, JUST WEEKS 1-4]

Demographics Measure (just week 1)

At week 8 only, participants will be asked the following questions (in addition to those previously approved):

- What is your total annual household income? (Less than \$20,000; \$20,000 \$39,999; \$40,000 \$59,999; \$60,000 \$79,999; \$80,000 \$99,999; \$100,000 \$149,999; \$150,000 or more; Prefer not to answer)
- To what extent did you participate in the study for each of the following reasons (answer scale is 1 (strongly disagree) to 5 (strongly agree): For fun; Was curious to learn about mental health; Really needed the money; Wanted the money, but didn't need it; Other [open text field]; Prefer not to answer

For the exit survey, participants will be asked to complete:

- Exit Survey (Control) [Control condition ONLY]
- Exit Survey (DIY) [DIY Tool, AI and DIY Tool, no AI conditions ONLY]

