#### **Randomization Procedures**

Once consenting to the study, upon beginning the REDCap screening survey, potential participants will automatically be randomly assigned to one of three conditions. This random assignment will not impact their screening process, eligibility, or the consent process. Their randomly assigned condition will not be revealed to them until after they consent to the study. Upon their consent, the information will be delivered to them via email, informing them of their assigned condition, outlining the study tasks and payment structure.

The three conditions are as follows: Control condition with psychoeducational reading material, a DIY worksheet, or a DIY tool with artificial intelligence, and are all concerned with the idea of thinking traps and learning how to apply the concept of cognitive reframing to situations in one's own life. Folks in both DIY tool conditions will be prompted to use their tools 3x a week, and all participants will be asked to respond to weekly surveys for the duration of 4 weeks.

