## **Control Psychoeducation**

At the start of participation after consenting, participants in the control condition will be asked to read the psychoeducation materials that describe types of cognitive restructuring and tips for practicing them in the document DIY Study – Psychoeducation.docx that has been uploaded to zipline.

5.2 Recording	gs. Does the research involve creati	ng audio or video recordings?	
No	→ If no, go to question 5.3.		
X Yes	Yes $\rightarrow$ If yes, verify that you have described what will be recorded in 5.1 and answer question a .		
<del></del>		sent for being recorded be obtained from subjects and any other	
	individuals who may be re	ecorded?	
		nail [contact] before submitting this application in Zipline. In il, include a brief description of the research and a note that	
		als will be recorded without their advance consent.	
	X Yes		

(5.3) MRI scans. Will any subjects have a Magnetic Resonance Imaging (MRI) scan as part of the study procedures?

This means scans that are performed solely for research purposes or clinical scans that are modified for research purposes (for example, using a gadolinium-based contrast agent when it is not required for clinical reasons).

X No → If no, go to question **5.4**.
Yes → If yes, answer questions **a** through **c**.

a.	Describe	the MR	scan(s	). S	pecifically	y :
----	----------	--------	--------	-------------	-------------	------------

- What is the purpose of the scan(s)? Examples: obtain research data; safety assessment associated with a research procedure.
- Which subjects will receive an MRI scan?
- Describe the minimum and maximum number of scans per subject, and over what time period the scans will occur. For example: all subjects will undergo two MRI scans, six months apart.

b. l	Jse of gadolinium. Will any of the MRI scans involve the use of a gadolinium-based contrast agent
	(GBCA?)

No Yes

→ If yes, which agents will be used? Check all that apply.

Brand Name	Generic Name	Chemical Structure
Dotarem	Gadoterate meglumine	Macrocylic
Eovist / Primovist	Gadoxetate disodium	Linear
Gadavist	Gadobutro	Macrocyclic
Magnevist	Gadpentetate dimeglumine	Linear
MultiHance	Gadobenate dimeglumine	Linear
Omniscan	Gadodiamide	Linear
OptiMARK	Gadoversetamide	Linear
ProHance	Gadoteridol	Macrocyclic
Other, provide name:		

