# Study 2 -

DIY Tool Metadata (both with AI and without AI)

In addition to metadata collected from the MHA website, metadata will also be collected from the DIY tool which is hosted on the Microsoft Azure platform. These specific variables will be measured:

- Engagement in length of time spent on the measure
- Completion rate of measure (% of measure completed)
- Dosage, in number of times/sessions using/visiting measure or psychoeducation
- Amount of use on the MHA website

Participants will be asked to complete the following measures in the screener:

- PHO-9
- GAD-7
- Hopefulness Item
- Emotion Mechanisms

At the end of weeks 1-4 and week 8 follow up, participants will be asked to complete the following measures:

- Questions Post DIY AI [DIY Tool, AI condition ONLY]
- PHQ-9

- GAD-7
- Hopefulness Item
- Emotion Mechanisms
- Competencies of Cognitive Therapy Scale Self Report
- Tool Use (sustain) [DIY Tool, No AI condition ONLY WEEKS 1-4, BOTH DIY TOOL CONDITIONS WEEK 8]
- Tool Use (AI) [DIY Tool, AI condition ONLY, JUST WEEKS 1-4]
- Demographic questions (JUST WEEK 1)

For the exit survey, participants will be asked to complete:

- Exit Survey (Control) [Control condition ONLY]
- Exit Survey (DIY) [DIY Tool, AI and DIY Tool, no AI conditions ONLY]
- (5.5) Data sources. For all types of data that will be accessed or collected for this research: Identify whether the data are being obtained from the subjects (or subjects' specimens) or whether they are being obtained from some other source (and identify the source).

If you have already provided this information in Question 5.1, you do not need to repeat the information here.

Surveys and screeners are completed by participants (MHA and TS consumers). Meta-Data is curated from each website (MHA and TS)

Focus group data is provided by participants.

Phase 3B Study 2: Screener and surveys are completed by participants. Meta-data is also curated from DIY tool website.

**5.6 Identifiability of data and specimens**. Answer these questions carefully and completely. This will allow HSD to accurately determine the type of review that is required and the relevant compliance requirements. Review the following definitions before answering the questions:

Access means to view or perceive data, but not to possess or record it. See, in contrast, the definition of "obtain".

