ENHANCING ENGAGEMENT WITH DIGITAL MENTAL HEALTH CARE

STUDY00010958

07/03/2024

NCT04507360

Aim 3B Statistical Analysis Plan. For Study 1, all research questions were examined via logistic regressions. We assessed whether participants' first condition (i.e., demographics survey or Next Steps survey) predicted the odds of disengagement. Within participants who completed the demographics survey, we examined whether the odds of disengaging and clicking a featured resource on the screening results page significantly differed for participants in the Tailored Resources to Demographics condition compared to control (i.e., Generic Response + Generic Resources). Within participants from the Next Steps survey condition, we tested whether engagement significantly differed for participants shown Tailored Response + Generic Resources, Generic Response + Tailored Resources to Desired Resources, and Tailored Response + Tailored Resources to Desired Resources compared to control. We aimed to identify the optimal tailoring strategy by comparing engagement across all tailoring conditions, with Tailored Resources to Demographics set as the reference group. For Study 2, research questions were examined via t-tests and Cohen's d effect sizes comparing engagement, short-term restructuring effectiveness, longer-term effectiveness (e.g., skill acquisition, reductions in depression and anxiety), and heterogeneous treatment effects by condition (i.e., control, DIY tool without AI, and DIY tool with AI).

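### No pre-treatment administration of the Competencies of Cognitive Therapy Scale, the evident instrument for Study 2's skill-acquisition outcome, is listed

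*Protocol*

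**What the plan says.** The SAP's Study 2 sentence states "For Study 2, research questions were examined via t-tests" and Cohen's d. Among the outcomes compared by condition it lists "longer-term effectiveness (e.g., skill acquisition, reductions in depression and anxiety". It names no instrument for skill, no covariates, and no choice between raw and change scores.

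Protocol section 5.1 (Study 2, Recruitment Procedures) and section 5.4 (Study 2) each itemise the measures. In 5.4 the screener list opens with "Participants will be asked to complete the following measures in the screener" and holds four entries: PHQ-9, GAD-7, the hopefulness item and emotion mechanisms. The list in 5.1 has the same four. The second battery opens with "At the end of weeks 1-4 and week 8 follow up, participants will be asked to complete the following measures" and adds the "Competencies of Cognitive Therapy Scale Self Report", with no restriction by arm. Section 4.4 counts six surveys after consent: weeks 1 to 4, the week 5 exit survey and week 8.

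On exposure, the Randomization Procedures say that the three conditions "are all concerned with the idea of thinking traps and learning how to apply the concept of cognitive reframing". The control paragraph says "At the start of participation after consenting, participants in the control condition will be asked to read the psychoeducation materials". Both tool arms are prompted to use their tool during each of the four weeks.

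**The concern.** The word acquisition suggests a gain from a starting point. Depression and anxiety, which the SAP names beside it, each have a pre-treatment score. On the listed schedule the skill scale does not.

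Three things would follow. The analysis could not adjust for the scale's own earlier score, which is usually the closest covariate. Starting skill would be unavailable as a moderator, although the SAP plans heterogeneous treatment effects and the intervention teaches a skill. Within-person change from before treatment could not be reported.

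The third loss matters because the control also teaches reframing. If the arms end level, post-treatment scores alone cannot tell whether everyone learned or nobody did. There is also a temptation to treat week 1 as the baseline, although it is measured after treatment has been offered.

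**Working it through.** **Is there room for an unlisted baseline survey after consent?** From section 4.4: 4 weekly surveys + 1 exit survey + 1 follow-up = 6, which reproduces the stated six. Control pay is 4 × $5 + $10 + $10 = $40. The tool arms can earn 4 × $5 more, giving $60. Both match the text, so no post-consent baseline survey is left. This says nothing about the screener, which section 8.2 places before consent.

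**Listed administrations (sections 5.1 and 5.4).**
- PHQ-9, GAD-7, hopefulness, emotion mechanisms: 1 before treatment, 5 after (weeks 1, 2, 3, 4 and 8).
- Competencies scale: 0 before treatment, 5 after.

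The overview in 5.1 says participants "complete the same list of measures for 4 weeks while using intervention". That could be read as carrying one list forward from screening, but the itemised lists differ and both omit the scale from the screener.

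**Exposure before the first score.** Controls are asked to read at the start, and the tool arms are prompted during week 1. Section 5.1 gives tool use as twice weekly in one place and three times weekly in others. Those passages must be reconciled, but either frequency puts prompts before the end of week 1.

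**Precision (illustration).** The documents give no effect size, SD, power or correlation, so there is no sample-size calculation to reproduce. Assumed: equal allocation, two-sided 5%, 80% power, one pairwise comparison, no multiplicity correction, no dropout. Let ρ be the correlation between baseline and later skill.
- Post scores only: (1.960 + 0.842) × √(2/n). At n = 100 this is 0.396.
- Baseline as covariate: multiply by √(1 − ρ²). At ρ = 0.3, 0.5, 0.7: 0.378, 0.343, 0.283.
- Change-score t-test: multiply by √(2(1 − ρ)). Same ρ: 0.469, 0.396, 0.307.

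Sections 2.1 and 4.1 put Study 2 at 250, while sections 1.6, 2.7 and 5.1 say 300. With 250 (83.3 per arm) the figures are 0.434 post-only and 0.414, 0.376 or 0.310 with the covariate.

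**Gain over covariates already collected.** Assume a composite of the four screener measures correlates r = 0.3 with later skill and g = 0.3 with baseline skill.
- Composite alone, n = 100: 0.396 × √(1 − 0.09) = 0.378.
- Baseline skill added: R² = (ρ² + r² − 2ρrg)/(1 − g²) = 0.138, 0.275, 0.499 at ρ = 0.3, 0.5, 0.7. Then 0.396 × √(1 − R²) = 0.368, 0.337, 0.280.

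**Week 1 as a substitute baseline.** Suppose the true difference is 0.40 and 25%, 50% or 75% of it is present by week 1. Change from week 1 would then show 0.40 × 0.75, 0.50 or 0.25 = 0.30, 0.20 or 0.10.

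**The case against.** **The screener lists are not exhaustive.** Section 2.2 makes eligibility depend on self-reported familiarity with reframing, yet neither list shows that question. At least one screening item is therefore collected but unlisted. The recruitment and screening file named in sections 4.2 and 4.6 is not available, and the survey count cannot close the gap because the screener precedes consent. This stands. A reader might infer that no baseline score exists. The documents support only that none is listed.

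**The instrument is inferred.** This also stands. The Competencies scale is the only named skill scale given to all arms, but the SAP does not make the link.

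**Exposure means offered, not used.** Controls are asked to read and tool users are prompted, and section 5.1 says engagement with such tools can be low. So a reader should not infer that everyone had practised by week 1. Low use still does not make week 1 a baseline, because it follows both randomisation and the offer of treatment.

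**The planned comparison is between arms.** A reader might infer that the missing score biases it. It does not: randomisation protects the comparison of later scores, and no passage promises within-person change on this scale. Nor would a baseline fully settle whether all arms learned or none did. No arm is untreated, so change over time would include retesting and time effects.

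**The precision gain is conditional.** It requires a second change, from a t-test to a covariate model. With a change-score t-test nothing is gained unless ρ exceeds 0.5. Selecting people with little familiarity could keep ρ near 0.3, where the gain is small. This stands and limits the weight of the point.

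**Conclusion.** The point holds in a limited form. Sections 5.1 and 5.4 agree that the Competencies scale is first given at the end of week 1, after all arms have been offered reframing content, and section 4.4 leaves no post-consent baseline survey. Whether the screener contained the scale without listing it is for the sponsor to confirm.

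If the gap is real, the valid result is a between-arm difference in post-treatment skill. The familiarity criterion restricts starting skill but does not measure it.

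At 100 per arm, the precision forgone relative to the planned t-test is 0.40 against 0.38, 0.34 or 0.28, depending on a correlation that the documents do not give. Relative to a model using the existing screener measures, it ranges from slight (0.378 to 0.368 at 0.3) to substantial (0.378 to 0.280 at 0.7). All these figures rest on the assumptions stated with the calculation. This is worth changing because it is cheap; the validity of the randomised contrast is not in doubt.

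**What to change.** The sponsor should first confirm which instrument measures skill acquisition and whether the screener contained it.

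**If enrolment is open and it did not:** give the scale once, after consent and before the email that reveals the condition. Section 8.7 places random assignment before consent but keeps it hidden until afterwards, so a score taken then cannot be influenced by knowledge of the arm. Compare arms with a linear model that includes this score as a covariate, not with an unadjusted or change-score t-test. Keep randomised participants who skip the form in the analysis.

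The cost is a few minutes per participant for a form already given five times, a slightly later condition email (section 8.7 values few delays), and possible priming of people chosen for low familiarity. Placing the scale in the screener avoids the extra step, but ineligible respondents would then also complete it.

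**If data are already collected,** as the SAP's past tense suggests: replace the unadjusted t-tests with a model adjusting for pre-treatment PHQ-9, GAD-7, hopefulness and emotion mechanisms, and label this as added afterwards. Report skill as post-treatment differences between arms. Do not use week 1 as a baseline or claim within-person acquisition. This costs only a model change and wording.
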